10.2 Secondary study parameter(s)

Descriptive analysis of participant demographics and outcomes will be conducted. Medians and interquartile ranges will be calculated for discrete data, such as scores from the questionnaires (IPAQ-SF, SQUASH, EQ-5D-5L, and OHS). These will be visualised through box plots. Mean and standard deviation will be calculated for continuous parameters.

To conduct aetiological analysis based on sample size, we will perform univariate and multivariate regression to assess for statistically significant confounders in relation to the questionnaire outcomes, such as PAEE and patient characteristics.

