1.3 Physical activity and common treatments for severe arthritis

Joint replacement is widely heralded as a safe and effective option for patients with end-stage arthritis, as patients report improved function and less pain. However, the statistic used to describe the success of the procedure is that of 'implant survival', which specifically ignores the more important metric of 'patient survival' (30). The two graphs below, from the National Joint Registry of England and Wales, illustrate this paradox: Figure 3A shows the unattractive higher mortality risks associated with total knee replacement, while Figure 3B shows the attractive low risk of revision surgery for the procedure.

[figure not shown]

Figure 3. Implant and patient survival post-knee replacement (30).

In earlier work from our group, we have published the substantial differences in gait characteristics between patients with different types of surgical procedures (31),(32),(33). However, any extrapolation from these small laboratory-based studies would be theoretical. Our best explanation for the profound difference in mortality, in the longer term, between more and less radical procedures is that patients who are allowed to retain more of their own bodies feel more normal and thus enjoy more activity. Alternatively, patients with large stiff metal implants substituting large parts of their femur and tibia are not expected to feel 'normal' ever again. To test this explanation, we propose to study physical activity of two groups of patients who participated in a previous study (34). In the current study, we want to explore whether physical activity levels varies between these two groups 15 years after their index surgery.

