2. OBJECTIVES

2.1 Primary Objective:

To compare the volume and intensity of physical activity 15 years after surgery in patients after hip resurfacing and total hip replacement.

2.2 Secondary Objective(s):

To explore the association between the participants' physical activity and functional outcome scores.

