10. STATISTICAL ANALYSIS

10.1 Primary study parameter(s)

Following the devices' return to the researcher, the recorded data will be downloaded and stored securely in a dedicated study folder on Rijnstate's digital network. The raw triaxial wrist and thigh acceleration data will be auto-calibrated to local gravitational acceleration (in g) and then converted to a Vector Magnitude (VM). VM, or Euclidean Norm, can be interpreted as the magnitude of acceleration the device was subjected to at each measurement, including gravitational acceleration. Non-wear detection procedures will be applied, and any such non-wear periods will be excluded from these analyses. The acceleration signal will be summarised to a common time resolution of one observation per minute and subjected to prediction models

to calculate physical activity energy expenditure, time in moderate-to-vigorous physical activity, and step count.

Raw accelerometry data will be processed using the R-project for Statistical Computing and open-source packages (R Foundation for Statistical Computing, Vienna, Austria). Statistical analysis will be conducted using STATA/SE version 17 (StataCorp, College Station, TX, USA). For descriptive statistics, we will report medians (interquartile ranges) or means (standard deviations) for continuous variables and proportions for categorical variables. To examine face validity and the performance of each multi-level linear regression model, we will conduct ANOVA repeat measures analysis to calculate Pearson's coefficient and Root Mean Squared Error metrics. Differential bias will be assessed by age, sex, and BMI categories.

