12. ADMINISTRATIVE ASPECTS, MONITORING AND PUBLICATION

12.1 Handling and storage of data and documents

All data handling and storage will comply with the EU General Data Protection Regulation and the Dutch Act on Implementation of the General Data Protection Regulation (Dutch: Uitvoeringswet AVG). All data collected during this study will be managed according to the FAIR principles in order to enhance and improve Findability, Accessibility, Interoperability and Reuse of research data.

All patient data will be handled confidentially. Each subject will be given an identification code and only the investigators involved in this study will have access to the subject identification code list which can be used to link the data to the patient. The code list and all raw patient data will be stored in a designated research folder on Rijnstate's local computer mainframe.

The Rijnstate coordinating investigator/project leader will collect the patient source data from the electronic patient records. These data comprise the participant's hospital identification number, age, gender, Body Mass Index (BMI), the presence and severity of any cardiovascular, pulmonary or neuromuscular diagnoses, and the use of medications for these diagnoses. After full data collection, data will be transferred to STATA/SE version 17 (StataCorp, College Station, TX, USA). In this spreadsheet the participant data will be non-identifiable/anonymous. All accelerometer and patient-related (questionnaire) data will be coded and securely shared with the UK investigators via Surf Filesender (<https://www.surf.nl/en/services/surffilesender>). All data collected during this study will be kept under secure conditions at Rijnstate Hospital for 15 years after the research has ended and then it will be destroyed. Any information collected will be treated as confidential and used only in this study unless otherwise specified. All source data relating to consented study participants will be stored and processed in line with Rijnstate Hospital requirements. All source data held in paper form (Informed Consents) will be scanned and securely stored as soon as possible after the participant has signed it. Paper copies will be stored in the secured research lockable cabinet at the department of Orthopaedics of Rijnstate.

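### Section 10.2 does not name implant group in the regressions of functional scores on activity, and its significance rule would often drop it if it were entered

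*Combined protocol and SAP*

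**What the plan says.** The secondary objective (section 2.2) is "To explore the association between the participants' physical activity and functional outcome scores". Its only analysis is in section 10.2, which plans "univariate and multivariate regression to assess for statistically significant confounders in relation to the questionnaire outcomes, such as PAEE and patient characteristics" and opens the sentence with "To conduct aetiological analysis based on sample size". No covariate list, significance level or selection procedure is given.

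Implant group does not appear in section 10 as a covariate, stratum or interaction. The factors that section 10.1 does name are for a check on measurement: "Differential bias will be assessed by age, sex, and BMI categories".

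Section 1.3 offers, as the authors' preferred explanation for outcome differences between more and less radical procedures, that "patients who are allowed to retain more of their own bodies feel more normal and thus enjoy more activity". It then says the present study is to "explore whether physical activity levels varies between these two groups". Section 8.1.2 describes the Oxford Hip Score (OHS) as covering walking, stairs, pain and limitation from the hip. Section 4 gives 34 resurfacing and 26 total hip patients.

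**The concern.** The analysis is labelled aetiological, so what the slope of score on activity means matters. Participants come from two groups defined by implant, and implant precedes both measurements. If one implant gives higher activity and also better scores, a slope over everyone combines two things: the association among patients with the same implant, and the gap between the two groups. A reader could then take an implant difference as evidence that activity and function go together.

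Choosing covariates by significance does not guard against this. The bias depends on the product of implant's shifts in activity and in score. The screen asks only whether implant's relation to the score reaches significance in a small sample.

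**Working it through.** The documents give no effect size, standard deviation, power or significance level for this analysis, so there is no figure of the plan's own to reproduce. All shifts and slopes below are assumptions, in within-implant SD units.

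**Inputs.** From section 4: 34 and 26, total 60. So p = 34/60 = 0.567 and p(1−p) = 0.2456. Section 8.2 speaks of 82 randomised but gives the same two arm sizes; I use their sum.

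**Step 1: slope without an implant term.** Let b be the within-implant slope, and dx and dy the implant differences in PAEE and in score. Then

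pooled slope = (b + p(1−p)·dx·dy) / (1 + p(1−p)·dx²).

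Example with b = 0 and dx = dy = 0.5: 0.2456 × 0.25 = 0.0614, and 0.0614 / 1.0614 = 0.058.

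The standard error is about 1/√57 = 0.132 for b = 0, and √(0.91/57) = 0.126 for b = 0.30.

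| Assumed shift in both | Pooled slope, b = 0 | Bias / SE | Pooled slope, b = 0.30 | Bias | Bias / SE |
|---|---|---|---|---|---|
| 0.2 SD | 0.010 | 0.08 | 0.307 | 0.007 | 0.06 |
| 0.5 SD | 0.058 | 0.44 | 0.340 | 0.040 | 0.32 |
| 0.8 SD | 0.136 | 1.03 | 0.395 | 0.095 | 0.75 |
| 1.0 SD | 0.197 | 1.49 | 0.438 | 0.138 | 1.09 |

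If implant shifts only the score, the bias is zero. If it shifts only PAEE by 0.5 SD with b = 0.30, the slope is 0.283. If the 0.5 SD shifts have opposite signs, it is 0.225.

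**Step 2: would a significance screen keep implant?** Assume two-sided 0.05. The standard error of the score difference is √(1/34 + 1/26) = 0.2605.

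- Univariate, true difference 0.5 SD: 0.5/0.2605 = 1.919, and Φ(1.919 − 1.960) = 0.48. Simulation (3,000 runs, b = 0.30) gave 47%.
- With PAEE in the model, b = 0.30 and dx = dy = 0.5, the implant coefficient shrinks to 0.5 − 0.30 × 0.5 = 0.35. Simulated retention was 26%.
- At 0.8 SD in both, retention was 87% by the univariate formula (85% simulated) and 53% simulated with PAEE in the model.
- The univariate test has 80% power only at (1.960 + 0.842) × 0.2605 = 0.73 SD.

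**Step 3: effect of forcing the term.** In the same simulation with b = 0.30, the mean slope with implant in the model was 0.304 at both 0.5 and 0.8 SD. Without it, the means were 0.345 and 0.400. The standard error rose from 0.1235 to 0.1277 (about 3%) at 0.5 SD, and from 0.1202 to 0.1284 (about 7%) at 0.8 SD.

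**The case against.** **Silence is not a plan to omit.** A reader might infer that the groups will be pooled without an implant term. The documents do not say so. The covariate wording in 10.2 is open and could include implant. Section 12.1, with "the presence and severity of any cardiovascular, pulmonary or neuromuscular diagnoses, and the use of medications for these diagnoses" alongside age, gender and BMI, lists what is taken from hospital records. It does not define the model's covariates, and implant would not need extraction because it is known from the earlier trial. This stands. The defect is that implant is not specified and is left exposed to a significance rule.

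**The rationale is a hypothesised chain.** A reader might also infer that the slope is confounded. Section 1.3 proposes that implant affects feeling normal, which in turn affects activity. It presents this as a hypothesis and says nothing about OHS or EQ-5D-5L scores. Under such a chain, activity and function are truly associated within implant groups, and the activity shift is smaller than the function shift. With b = 0.30 and a function shift of 0.5 SD, the activity shift is 0.15 SD. The pooled slope is then (0.30 + 0.2456 × 0.5 × 0.15)/(1 + 0.2456 × 0.15²) = 0.317, a bias of 0.017. With a 1.0 SD function shift it is 0.366, about half a standard error. This stands too: the confounding is conditional and may be slight.

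**The objective asks about participants overall.** An unadjusted association is a legitimate exploratory answer, and adjusting for implant changes the quantity estimated. This stands in part. It is a reason to allow both slopes to be shown. It does not justify leaving the choice to a p-value in an analysis called aetiological.

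**Participation may be below 60.** At n = 40 the standard error is 1/√37 = 0.164, and the 0.8 SD bias of 0.136 falls below it. That is correct, but fewer participants also make the screen less likely to keep implant.

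Randomisation in the earlier trial does not settle the matter. It protects the comparison of implants, not the regression of one later measurement on another.

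**Conclusion.** The point holds in a limited form. Section 10.2 does not specify implant group, and its significance rule would keep a true 0.5 SD implant difference only about half the time or less at n = 60. Whether leaving implant out biases the slope depends on implant shifting both activity and score, which is plausible from section 1.3 but not quantified anywhere. For equal shifts in the same direction, the bias is under half a standard error at 0.5 SD. It is about one standard error at 0.8 SD if there is no within-implant association, and at about 1.0 SD if the within-implant slope is 0.30. The documents do not support a claim that the plan excludes implant, nor that the slope is confounded. This is a nearly free improvement to an exploratory secondary analysis and does not touch the primary comparison.

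**What to change.** In section 10.2, state that each regression of a functional score on activity includes implant group as a pre-specified fixed term, retained whatever its p-value, and that the reported slope is the within-implant association. The unadjusted slope may be shown alongside it, labelled as such. The cost is one clause and one degree of freedom, plus about 3% in standard error at 0.5 SD shifts (7% at 0.8 SD). No new data are needed, since each participant's implant is known from the earlier trial.

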11. ETHICAL CONSIDERATIONS

11.1 Regulation statement

The study will be conducted according to the principles of the Declaration of Helsinki (Seoul, Korea, October 2008) and in accordance with the Dutch Medical Research Involving Human Subjects Act (WMO).

11.2 Recruitment and consent

Participants will be approached by their treating orthopedic surgeon using an introduction letter and a Patient Information Form (PIF) which includes the Informed Consent Form (IC, see Appendix E). One week after sending the PIF/IC, the coordinating researcher will contact the patient by phone to ask whether the patient has any questions about the study, and whether he/she is willing to participate. No pressure will be placed on any individual to participate; it will be made clear that participation is entirely voluntary and that participation can cease at any time. Participants who are will be asked to sign and date the Informed Consent form and return it to the researcher in a pre-paid envelope.

11.3 Benefits and risks assessment, group relatedness

Benefits

Participating in this study has no direct benefits for the participants, but it may provide participants some insight into their own physical activity.

Risks

Participants in this study will be asked to continuously wear a triaxial accelerometer for ten days and nights on their non-dominant wrist and for 48 hours on their thigh. In some instances, individuals may experience minor skin irritation or develop a localised rash from wearing the wrist strap. This is similar to cases where one starts to use a new (regular) watch or other wrist-worn device. Leaving the monitor off for one night should alleviate this. If the strap is damp, drying both the skin and strap can also reduce irritations. However, if the irritation persists, participants are asked to remove the monitor and return it to the researcher in the prepaid padded envelope. If the irritation does not resolve on its own, a small amount of moisturising skin cream (e.g. Sudocrem, Nivea Soft, Bepanthen Zalf) may be applied to the affected area. This can be obtained without prescription from a pharmacist. The same treatment approach is recommended if minor skin irritation or a localised rash arises from using 3M Tegaderm Film strips (3M, UK), which will be used to secure the Axivity AX3 accelerometers on participants' thighs.

11.4 Incentives

Participants will not receive any incentives for their participation.

12. ADMINISTRATIVE ASPECTS, MONITORING AND PUBLICATION

12.1 Handling and storage of data and documents

All data handling and storage will comply with the EU General Data Protection Regulation and the Dutch Act on Implementation of the General Data Protection Regulation (Dutch: Uitvoeringswet AVG). All data collected during this study will be managed according to the FAIR principles in order to enhance and improve Findability, Accessibility, Interoperability and Reuse of research data.

All patient data will be handled confidentially. Each subject will be given an identification code and only the investigators involved in this study will have access to the subject identification code list which can be used to link the data to the patient. The code list and all raw patient data will be stored in a designated research folder on Rijnstate's local computer mainframe.

The Rijnstate coordinating investigator/project leader will collect the patient source data from the electronic patient records. These data comprise the participant's hospital identification number, age, gender, Body Mass Index (BMI), the presence and severity of any cardiovascular, pulmonary or neuromuscular diagnoses, and the use of medications for these diagnoses. After full data collection, data will be transferred to STATA/SE version 17 (StataCorp, College Station, TX, USA). In this spreadsheet the participant data will be non-identifiable/anonymous. All accelerometer and patient-related (questionnaire) data will be coded and securely shared with the UK investigators via Surf Filesender (<https://www.surf.nl/en/services/surffilesender>). All data collected during this study will be kept under secure conditions at Rijnstate Hospital for 15 years after the research has ended and then it will be destroyed. Any information collected will be treated as confidential and used only in this study unless otherwise specified. All source data relating to consented study participants will be stored and processed in line with Rijnstate Hospital requirements. All source data held in paper form (Informed Consents) will be scanned and securely stored as soon as possible after the participant has signed it. Paper copies will be stored in the secured research lockable cabinet at the department of Orthopaedics of Rijnstate.

Before the study commences, the UK partner will sign a Data Transfer Agreement (Stichting Topklinische Ziekenhuizen template 'Beschikbaarstelling persoonsgegevens/versie maart 2021') with Stichting Rijnstate Ziekenhuis.

Privacy of the participants

Both the GENEActiv triaxial accelerometer and Axivity AX3 triaxial accelerometer do not store any personal identifiable data. A code number on each monitor is matched with a participant ID number. The key to this code is known by the research team only. The participants' personal details are stored separately. Other security mechanisms are also used to protect the participants' privacy. For example, both types of accelerometer do not have GPS and do not measure the location of where the participant is. The accelerometers are only measuring body movement i.e. whether it moves up/down, forward/back and side-to-side. Once the movement data is uploaded, only the research team will be able to match the movement data to other patient information.

12.2 Monitoring and Quality Assurance

Monitoring of this study will take place during the total study duration according to guidelines set out by the Samenwerkende Topklinische Ziekenhuizen (STZ) and as described in Standard Operating Procedure 'STZ SOP VC12 Monitoringplan' (STZ version 21-02-2019; Rijnstate version 8-5-2019). Monitoring will be performed by Rijnstate's local Research Ethics Office.

12.3 Amendments

Amendments are changes made to the research after a favourable opinion by the accredited METC has been given. All amendments will be notified to the METC that gave a favourable opinion. Non-substantial amendments will not be notified to the accredited METC and the competent authority, but will be recorded and filed by the sponsor.

12.4 Annual progress report

The sponsor/investigator will submit a summary of the progress of the trial to the accredited METC once a year. Information will be provided on the date of inclusion of the first subject, numbers of subjects included and numbers of subjects that have completed the trial, serious adverse events/ serious adverse reactions, other problems, and amendments.

12.5 Temporary halt and (prematurely) end of study report

The investigator/sponsor will notify the accredited METC of the end of the study within a period of eight weeks. The end of the study is defined as the last patient's last visit.

The sponsor will notify the METC immediately of a temporary halt of the study, including the reason of such an action. In case the study is ended prematurely, the sponsor will notify the accredited METC within 15 days, including the reasons for the premature termination.

Within one year after the end of the study, the investigator/sponsor will submit a final study report with the results of the study, including any publications/abstracts of the study, to the accredited METC.

12.6 Public disclosure and publication policy

This study will be prospectively registered in a public trial registry before the first patient is recruited. All data will be the property of Rijnstate. Publication will be the responsibility of the coordinating and principal investigators. It is planned to publish the results of this study in a peer-reviewed journal and to present results at national and international meetings. It will not be possible to identify any individuals from any publication or presentation.

13. STRUCTURED RISK ANALYSIS

According to the Dutch Federation of University Medical Centers, the risk in this study is negligible ("verwaarloosbaar risico") because there is only a small risk of minimal damage ("kleine kans op lichte schade"). Patients will be asked to wear an accelerometer on their wrist for ten days, and to simultaneously wear one accelerometer on their surgical thigh for 48 hours.

Both accelerometers collect physical activity data automatically. Additionally, participants will be asked to complete four paper questionnaires at home (duration: 15 minutes).

13.1 Potential issues of concern

N/A.

13.2 Synthesis

Participating in this study has no direct benefits for the participants. Participants who consent to participate will be asked to:

1. Complete 4 paper questionnaires (duration: 15 minutes).
2. Wear the GENEActiv tri-axial accelerometer on the wrist continuously for ten days and nights, and wear one Activity Ax3 Logging tri-axial accelerometers on the surgical thigh continuously for 48 hours. Wearing accelerometers is common, usually well tolerated and there are no documented risks of wearing in particular or physical activity monitors in general.

